### 9.2 Secondary and other study parameters

Differences in (semi-)continuous variables between the two treatment groups (such as the VAS, TcpO2 and quality of life scores) will be analysed with the Student t-test in case of normally distributed data and otherwise the non-parametric Mann-Whitney U test, after correcting for baseline differences, if any.

Time to complete wound healing will be estimated using Kaplan-Meier survival analysis and differences between the groups will be analysed using the log-rank test. Changes over time of TcpO2 and quality of life scores will be analysed using the Wilcoxon test. Potential confounding factors will be adjusted using Cox proportional hazards regression modelling.

The economic evaluation of additional HBOT will be performed as a cost-effectiveness analysis from a societal perspective. Additionally, a cost-utility analysis will be performed with the costs per quality adjusted life-year (QALY) as outcome. As the time horizon is restricted to 12 months, no discounting (of costs and effects) will be performed.

The EQ-5D is used to generate health status scoring profiles over time, which will subsequently be translated in QALYs by applying time trade-off based health utility algorithms and assuming that interpolation between successive measurements best reflects a patient's health status during the year. Sensitivity analyses will be performed to account for sampling variability, for plausible ranges in unit costs, and for different health

utility algorithms. In addition, a budget impact analysis will be undertaken to assess the possible cost savings of HBOT if applied to all eligible patients on a national scale.

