### 3. STUDY DESIGN

Multinational randomized clinical trial with an adaptive (multi-arm, multi-stage; MAMS) design, with a follow-up of 12 months, following the (extended) CONSORT-statement. We will have four study arms and two stages (one interim and one final analysis; see figure 1 below). Patients will be randomized to receive standard treatment with 0, 20, 30 or 40 HBOT treatments.

The more efficient MAMS design (Sydes 2018, Sydes 2012, Wason 2012) for clinical trials includes a planned interim analysis, based on which only the best performing study arms will be chosen to continue. This will reduce the total number of patients required and the number of patients receiving an ineffective treatment, because after the interim analysis no patients will be included in less effective treatment arms.

[figure not shown]

Figure 1 Flow of patient inclusion and analysis

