## 5. TREATMENT OF SUBJECTS

### 5.1 Investigational product/treatment

Patients allocated to the intervention group will receive 20, 30 or 40 sessions of HBOT adjunctive to standard care, as determined by the randomisation. A HBOT session will take 90 to 120 minutes at 2.2-2.5 ATA. Besides the 90-120 minutes of treatment, approximately 20 minutes are required for compression and decompression. During the treatment session the patients will breathe 100% FiO2 except for 3 blocks of 5 minutes during which atmospheric air will be administered to prevent oxygen intoxication. This HBOT-regimen has been approved by the hyperbaric medicine specialists from all contributing HBOT-centers as the optimum and safest HBOT procedure for these patients. Patients will either lay in bed or sit in a chair during the session. At least for the first time, cabin personnel will accompany patients in the cabin and instruct them about the use of the oxygen masks or hoods. The cabin will be pressurized gradually in about 10 minutes. Subsequently, the supervising staff member will supply patients with masks through which the oxygen will be administered. The staff member will then leave the cabin, but will remain in constant contact with the patients through cameras and microphones. In case of adverse events requiring termination of the session, patients will be able to leave the cabin after a short decompression period. After the treatment, the cabin will be decompressed in about 10 minutes.

HBOT will be administered in a hyperbaric chamber. HBOT is preferably given 5 times per week, but at least 3 times per week, until the total number of sessions has been reached. To minimize interruption of HBOT and masking of the effect by additional vascular interventions, any (additional) (endo)vascular procedure will preferably be performed after randomisation but before the start of HBOT treatment. In case a vascular intervention is required (due to progression of the disease) while the patient is undergoing the HBOT sessions, these are interrupted for the period of the vascular intervention and continued directly afterwards until completion of the sessions.

[figure not shown]

Figure 3 Example of HBOT tabel

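### Section 9.2 compares two groups in a four-arm trial and names no regimen for the economic evaluation, so the secondary contrasts do not fit the question of how many sessions

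*Protocol*

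**What the plan says.** Section 3 sets out the design: "We will have four study arms and two stages", and "Patients will be randomized to receive standard treatment with 0, 20, 30 or 40 HBOT treatments". Section 4.4 compares each HBOT group with control, closes or continues each one on its own result, and prefers the fewest sessions if several are superior. Section 9.1 speaks of the study arms when it describes the interim test of the primary outcome.

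Section 9.2 uses different terms. For pain, TcpO2 and quality of life it plans to analyse "Differences in (semi-)continuous variables between the two treatment groups". These "will be analysed with the Student t-test in case of normally distributed data and otherwise the non-parametric Mann-Whitney U test". For time to wound healing it says only that "differences between the groups will be analysed using the log-rank test", with no number of groups. On costs it states: "The economic evaluation of additional HBOT will be performed as a cost-effectiveness analysis". The budget impact analysis likewise refers to HBOT without a number of sessions.

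Section 5.1 uses the singular for all three active regimens: "Patients allocated to the intervention group will receive 20, 30 or 40 sessions of HBOT adjunctive to standard care". Section 9 places all analyses under intention to treat and makes no exception for arms closed at the interim.

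**The concern.** The number of groups in section 9.2 does not match the number of arms in the design, and the named tests take exactly two samples. This is more than detail left for later, because the protocol states a comparison that its own design does not supply.

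What is at stake is the question the trial was set up to answer. Section 2 aims to establish the optimal number of sessions, and the Summary asks whether and how many sessions may be (cost-)effective. Cost-effectiveness is also part of the Summary's primary objective. A single comparison of HBOT with no HBOT cannot answer a question about 20, 30 or 40 sessions. If the contrast is still open when the interim results are known, it could also be chosen after seeing which arms survived.

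**Working it through.** **1. The plan's own arithmetic is for four separate arms.** Section 4.4 gives 68 patients per group per stage, a maximum of 544, and 573 after 5% loss to follow-up.
- 68 × 4 arms × 2 stages = 544.
- 544 / (1 − 0.05) = 572.6, rounded up to 573.

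Both figures reproduce, and only with four arms.

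**2. When are there two groups?** The outcomes that section 4.4 allows are:

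| Interim outcome | Groups without pooling |
|---|---|
| Stop for superiority | 4 (68 each) |
| Continue, no HBOT arm closed | 4 |
| Continue, one HBOT arm closed | 3 |
| Continue, two HBOT arms closed | 2 still recruiting in stage 2 |

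Only the last row gives two groups without pooling. Even there, four arms have been randomised, and section 9.2 does not say what happens to patients in the two closed arms.

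**3. What would a pooled HBOT group contain?** This step assumes that the trial reaches stage 2 with 68 per open arm per stage, and that all HBOT patients are pooled. With k closed arms the pooled HBOT group has 68k + 136(3 − k) patients, of whom 68k come from closed arms. Control has 136.

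| Arms closed (k) | HBOT patients | From closed arms | Share |
|---|---|---|---|
| 0 | 408 | 0 | 0% |
| 1 | 340 | 68 | 20% |
| 2 | 272 | 136 | 50% |

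Of the 136 controls, 68 (50%) would have been randomised after the closed arms had stopped recruiting.

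**4. Which regimen would the pooled group represent?** The mean number of allocated sessions is:
- no arm closed: (20 + 30 + 40) / 3 = 30;
- 20-session arm closed: (68×20 + 136×30 + 136×40) / 340 = 10,880 / 340 = 32;
- 40-session arm closed: (68×40 + 136×30 + 136×20) / 340 = 9,520 / 340 = 28.

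The average therefore depends on which arms close, and it is an average over regimens rather than a result for any one of them.

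**5. What does separating the arms cost in precision?** Standard errors are in SD units, with no arm closed:
- pooled: √(1/136 + 1/408) = 0.099;
- one arm against control: √(2/136) = 0.121.

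The ratio is 0.121 / 0.099 = 1.22, so per-arm intervals are about 22% wider. For a closed arm against stage-1 controls the standard error is √(2/68) = 0.171, which is 1.41 times that of an arm that continues.

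**The case against.** A reader might infer that section 9.2, applied as written, pools the three HBOT arms. The text does not go that far. It has no pooling rule and does not define its two groups. Control against one surviving arm is also two groups, and pairwise comparisons would fit the named tests. The phrase covers only the (semi-)continuous outcomes. It is not used for wound-healing time or in the economic paragraph, where additional HBOT may simply name the intervention. These limits stand, so the consequences in steps 3 and 4 of the working are conditional. They do not remove the mismatch, because the surviving-arm reading works in only one interim outcome and pairwise testing leaves the intended pairs unstated.

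A reader might also infer that pooling necessarily loses power. That depends on assumed effects, since the protocol gives none for these outcomes. Take no arm closed and a two-sided 5% test. With effects of 0, 0.15 and 0.30 SD for 20, 30 and 40 sessions, power is 33% pooled (0.15 / 0.099) against 70% for 40 sessions alone (0.30 / 0.121). With 0.30 SD in every arm the order reverses, to about 86% pooled against 70%. Power is therefore not the argument.

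Nor do the documents support a stated error in the cost per QALY. The pooled mean of 30 sessions is 1.5 times 20 and 0.75 times 40, but turning this into cost needs proportional costs and full attendance. The protocol gives no unit costs or attendance, and its perspective is societal.

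Finally, multiplicity control for secondary outcomes is commonly left to the SAP, so its absence here is no fault.

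**Conclusion.** The point holds as a contradiction within the protocol: section 9.2 names two groups and two-sample tests, while sections 3 and 4.4 describe four arms, each HBOT arm being judged separately against control. The economic evaluation and budget impact name no regimen, although the protocol asks how many sessions are (cost-)effective.

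Pooling is a possible reading, supported by the single intervention group in section 5.1 and the unqualified intention-to-treat statement in section 9, but it is not a stated rule. The 20% and 50% shares rest on three assumptions: pooling, reaching stage 2, and 68 patients per open arm per stage. The outcomes are secondary and the primary comparison is not affected. The text should still be corrected before interim results are known, because cost-effectiveness by number of sessions is central to the trial's purpose.

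**What to change.** In section 9.2, replace the two-group phrase with wording such as: between each HBOT arm and the control patients randomised concurrently with it. State how stage is handled, in one of two ways:
- compare arms closed at the interim with stage-1 controls only, which keeps the t-test and Mann-Whitney options usable arm by arm; or
- fit one joint model with arm as a factor and adjustment for stage. Without the stage term, such a model would compare closed arms with controls recruited later.

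Name the same contrasts for time to wound healing.

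For the economic evaluation, report costs and QALYs separately for 0, 20, 30 and 40 sessions, with incremental cost-effectiveness by regimen, and say which regimen the budget impact assumes. Setting all four regimens side by side needs a common comparator, so stage must be handled there too. A multiplicity adjustment for these secondary outcomes is optional. A pooled HBOT comparison could be kept if labelled as supplementary.

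The cost is an amendment to the text and some added analysis, with no new data and no change in sample size. The downside is wider intervals: about 22% wider than pooled if no arm closes, and wider still for a closed arm set against stage-1 controls.

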**SUMMARY**

**Rationale:** Diabetes is a major healthcare problem with a high incidence and morbidity. Diabetic foot ulcers (DFUs) are a major complication of diabetes, often associated with peripheral arterial occlusive disease. Currently available evidence shows HyperBaric Oxygen Therapy (HBOT) can reduce major amputation rate, but clinicians remain sceptical about the (cost-) effectiveness and feasibility of HBOT for ischemic DFUs in clinical practice. Therefore, international vascular surgeons and HBOT-physicians feel a strong need for a sufficiently powered clinical trial to determine whether and how many HBOT-sessions may be a (cost-) effective adjunctive treatment to ischemic DFUs.

**Objective:** The primary objective is to assess the (cost-) effectiveness of HBOT in addition to standard wound care and vascular surgical treatment for patients with a DFU and leg ischemia.

**Study design:** An international, multi-arm multi-stage (MAMS) design is chosen to conduct an efficient randomised clinical trial. At a planned interim analysis the best performing study arm(s) will be chosen to continue.

**Study population:** We need up to 544 patients with a Meggitt-Wagner stage 3 or 4 DFU and proven peripheral ischaemia.

**Intervention:** Patients will be randomised to receive standard care (wound treatment and surgical interventions following international guidelines) with either 0, 20, 30 or 40 sessions of HBOT. These sessions will comprise 90-120 minutes of HBOT at a pressure of 2.2-2.5 ATA according to international standards.

**Main study parameters/endpoints:** Primary endpoints are amputation rates and amputation-free survival after 12 months. Secondary objectives are wound healing, health-related quality of life and cost-effectiveness of the interventions.

**Nature and extent of the burden and risks associated with participation, benefit and group relatedness:** All patients will receive standard wound care and (if possible) endovascular or surgical revascularization, irrespective of their allocation. HBOT is a generally accepted and reimbursed indication for the treatment of DFUs. The risks of HBOT are regarded as low. Patients in the HBOT groups will undergo 20, 30 or 40 HBOT sessions. Patients will be asked to fill in questionnaires at four time points, and to score their pain weekly during the first 8 weeks. Three visits to their outpatient surgical clinic will be scheduled, which do not deviate from usual care.

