### 7.3 Study procedures

Patients from each (remaining) study arm will be monitored up to 36 months after randomisation. At the start of the trial, patients' baseline characteristics will be obtained. Pain scores will be collected through first phase of the trial. Questionnaires will be completed at baseline and will be sent to the patients' home after 3 months and 1 year.

Amputation rate, ulcer recurrence, additional interventions, mortality, adverse events and costs will be monitored after 1 year and 3 years.

Assessment	Before randomisation	Week 1-8, once a week	After 3 months	After 1 year	After 3 years
Patient characteristics	*				
Meggitt-Wagner classification	*		*	*	
Wound measurements	*				
Ankle blood pressure	*		*	*	
Toe systolic pressure	*		*	*	
TcPO2	*		*	*	
VAS		*	*	*	
Freedom of amputation			*	*	*
Complete ulcer healing			*	*	*
Recurrent ulcer			*	*	*
Nr of additional vascular events		*	*	*	*
Adverse events		*	*	*	
Patient's out of pocket expenses			*		
Questionnaires	*		*	*	*

*Table 1 Assessments and follow-up*

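### Section 9.2 corrects TcpO2 and quality-of-life scores for baseline only when a difference is present, by no stated criterion or method, and so forgoes precision that always adjusting would give

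*Protocol*

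**What the plan says.** Protocol section 9.2 covers (semi-)continuous outcomes and names the VAS pain score, TcpO2 and quality of life as examples. It states "quality of life scores) will be analysed with the Student t-test in case of normally distributed data" and, for other data, "otherwise the non-parametric Mann-Whitney U test, after correcting for baseline differences, if any". It gives no threshold for a baseline difference and no method of correction.

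The same section adds, for change over time in TcpO2 and quality of life, "quality of life scores will be analysed using the Wilcoxon test". The only regression it names is in "Potential confounding factors will be adjusted using Cox proportional hazards regression modelling", a model for time-to-event data.

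On what is measured at baseline:
- **Quality of life:** section 7.3 says "Questionnaires will be completed at baseline", and Table 1 marks the questionnaires before randomisation.
- **TcpO2:** Table 1 marks it before randomisation. Section 7.1.2 makes it subject to equipment being available.
- **Pain:** section 7.3 says "Pain scores will be collected through first phase of the trial". The Summary asks patients "to score their pain weekly during the first 8 weeks". The VAS row of Table 1 is blank before randomisation.

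QALYs are treated in a separate economic paragraph of section 9.2, which derives them from EQ-5D by "assuming that interpolation between successive measurements best reflects a patient's health status during the year" and does not mention baseline utility.

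**The concern.** Patients are randomised, so any baseline difference between arms is chance, and finding or not finding one is a poor reason to adjust or not. Adjustment helps because the baseline value predicts the outcome, and it does so equally in trials where the arms happen to match. A rule triggered by observed imbalance therefore uses the covariate in few trials and discards it in the rest.

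The rule is also undefined. Two analysts could follow the sentence and obtain different estimates, because neither the trigger nor the correction is fixed. The named tests have no covariate term, so the correction has to happen in an unnamed prior step.

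At stake are the precision of the TcpO2 and quality-of-life comparisons and the prespecification of their analysis. Quality of life is a listed secondary objective in section 2.

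**Working it through.** **Inputs from the documents.** Section 4.4 gives 68 patients per group per stage. The maximum reproduces: 68 × 4 arms × 2 stages = 544. An arm that runs through both stages has 68 × 2 = 136. Section 9 reports 95% confidence intervals, which corresponds to a two-sided 5% test.

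**Assumptions.** The documents give no SD, correlation or power for any continuous outcome. I take r from 0.3 to 0.7 and, for power, a true difference of 0.3 SD. For the conditional rule I take a baseline test at two-sided 5%. That is one reading of the sentence, not its text.

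**Variance of the arm difference, relative to no adjustment.**
- Analysis of covariance always: 1 − r².
- Change scores always: 2 − 2r.
- Analysis of covariance only when the baseline test is significant: the share of the gain that is kept is E[Z²; |Z| > 1.96] = 2 × (1.96 × 0.0584 + 0.025) = 0.279. The ratio is therefore 1 − 0.279r², and about 72% of the gain is lost. Simulation gave 25% to 31% kept.

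| r | ANCOVA always | Conditional on 5% test | Change scores |
|---|---|---|---|
| 0.3 | 0.91 | 0.975 | 1.40 |
| 0.5 | 0.75 | 0.930 | 1.00 |
| 0.7 | 0.51 | 0.863 | 0.60 |

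Simulation with 40,000 trials per cell gave 0.98, 0.93 and 0.86 for the conditional rule.

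**Power at 136 per arm, 0.3 SD.** The noncentrality is 0.3 × √(136/2) = 2.474.
- Unadjusted: Φ(2.474 − 1.96) = Φ(0.514) ≈ 70%.
- ANCOVA at r = 0.5: 2.474/√0.75 = 2.857, and Φ(0.897) ≈ 81%.

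Simulated power:

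| r | Unadjusted | Conditional | ANCOVA always |
|---|---|---|---|
| 0.3 | 69% | 69% | 73% |
| 0.5 | 70% | 71% | 81% |
| 0.7 | 70% | 72% | 93% |

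For an arm stopped at the interim, with 68 per arm and r = 0.5, the figures are 41%, 41% and 51%.

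**Type I error.** Under the conditional rule with regression adjustment, the simulated two-sided error was 4.9%, 4.2% and 3.5% at r = 0.3, 0.5 and 0.7. A second run gave 4.7%, 4.4% and 3.6%. The rule is conservative.

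**Pain.** Section 9.2 includes the VAS among the outcomes to be corrected for baseline. Table 1 starts VAS collection in weeks 1 to 8. No score before randomisation is scheduled, so there is nothing to correct with.

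**The case against.** The strongest objection is that the calculation rests on a rule the protocol does not contain. Section 9.2 names no baseline test and no 5% threshold. Read literally, any non-zero difference would be corrected, and with a continuous score that is nearly always. If the correction were then a regression on baseline, the loss would largely disappear. This stands as a limit on the size claimed. It does not rescue the sentence, which names no method that would adjust efficiently.

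A second objection is that the tests come after a correction, so they could be run on change scores. That fits the wording. At r = 0.7 change scores give 89% power, against 70% unadjusted and 93% for ANCOVA. At r = 0.5 they are no better than no adjustment, and below 0.5 they are worse. They never beat ANCOVA, because (2 − 2r) − (1 − r²) = (1 − r)², which is never negative.

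Third, 136 per arm is a best case. It needs both arms to pass the interim with complete data, and TcpO2 depends on equipment. This stands.

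A reader might infer more than the documents support:
- **That precision is lost for pain.** It is not, because no baseline VAS is scheduled. The fault there is a conflict between two sections.
- **That the rule mishandles QALYs.** The sentence does not govern them. Interpolating from baseline does carry baseline utility into the QALY, but the economic paragraph is merely silent on adjusting for it, and an analysis plan may supply that.
- **That most of the precision is given up.** Most of the *gain from adjustment* is lost under the 5% reading. The gain itself exceeds half the variance only when r is above about 0.71.

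**Conclusion.** The point holds for TcpO2 and quality-of-life scores. The protocol fixes a correction that depends on chance imbalance and leaves both trigger and method undefined, although the baseline values are collected. This is a flaw in a stated method, not a detail left for later.

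Always adjusting would reduce the variance of the arm difference by 9% to 49% for r of 0.3 to 0.7. Read as a 5% baseline test, the rule loses about 70% of that reduction. Read as change scores, it does worse than no adjustment when r is below 0.5. The 70%, 71% and 81% power figures rest on the assumed r of 0.5, the assumed 0.3 SD difference, 136 per arm and the 5% reading.

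The consequence is limited. These outcomes are secondary and have no stated power target. The amputation endpoints, stopping rules and sample size are untouched. Under the 5% reading with regression adjustment, the error rate is below nominal, so the cost is lost power and an undefined analysis rather than false positives.

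For pain, sections 7.3 and 9.2 contradict each other and must be reconciled.

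**What to change.** Replace the sentence in section 9.2 with:

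> TcpO2 and each quality-of-life score at each time point will be compared by linear regression (ANCOVA) with arm, the baseline value and the stratification factors as covariates, whether or not the arms differ at baseline, with robust or bootstrap intervals if residuals are skewed.

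The stratification factors are those in section 7.2: centre, and inclusion with a minor amputation. This costs wording only, since the baseline data are already scheduled.

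For the VAS, either schedule a score before randomisation in Table 1 or remove the VAS from the baseline correction. The first adds one measurement and cannot be supplied for patients already randomised. The second costs nothing.

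As a recommendation only, include baseline EQ-5D utility as a covariate when QALYs are compared.

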The largest and most recent DAMOCLES trial on HBOT for ischemic DFUs (Santema 2018a) showed some promising results for HBOT as an adjunctive treatment for patients with ischemic DFUs. However, the treatment effect was not convincing, due to the limited number of patients available for inclusion in a single country, as well as the inclusion of relatively superficial, uninfected (Meggitt-Wagner class 2) DFUs (Santema 2018b). They found 10% fewer major amputations after 12 months in patients treated with HBOT in their intention-to-treat analysis, but this was not statistically significant. In the per-protocol analysis a significant reduction of major amputations (17%) observed. Amputation-free survival (AFS) after HBOT was 13% higher in the intention-to-treat analysis, which was not statistically significant. In the per-protocol analysis the AFS was significantly (26%) higher as opposed to standard treatment. No significant effect was found on complete ulcer healing in neither the intention-to-treat nor the per-protocol analysis.

The recent meta-analysis (Brouwer 2020) of currently available evidence shows that HBOT may lead to a 15% reduction of major amputation rate, but shows no effect on minor amputation, CUH, or mortality. To date, substantial scepticism still exists among clinicians due to the limited and conflicting evidence for its (cost-)effectiveness to promote wound healing and prevention amputations or amputation-free survival. Hence, a strong need is felt internationally among vascular surgeons and HT-physicians for a sufficiently powered clinical trial that is able to determine whether HBOT is a (cost-)effective treatment for ischemic DFUs.

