### **4.4 Sample size calculation**

The primary outcome is the probability of amputations after 12 months. The meta-analysis showed a 15% difference (11% vs. 26%; Brouwer 2020) of amputations between patients treated with HBOT and patients treated conservatively. The sample size calculation is based on a one-sided type I error of 5% and a power of 90% to control for a type 2 error. A

generalization of the power requirements for testing multiple active treatments to one control group was used as proposed by Dunnett (Dunnett 1984).

The critical values for continuation of a treatment arm are odds ratios of 0.76 and 0.352, which are in accordance with a drop in amputations from 26% to 21% and to 11%. If the difference is <5% the HBOT treatment arm is deemed futile, while a difference of 15% or higher is deemed superior. Based on these critical values the required number of patients in each group in each stage is 68, leading to a required maximum number of 544 patients. The sample size calculation is based on a generalization of Whitehead and Jaki (Whitehead 2009, Jaki 2019). Taking into account a possible loss to follow-up of 5%, we will need a total of (up to) 573 patients.

This leads to the following stopping rules and possible scenarios after the interim analysis (using the chi-square test for differences in percentages between the groups) (see figure 2 below):

- 1) If one of the HBOT treatment groups leads to a significantly less than 5% improvement in amputation rate as compared to controls (based on the expected 26% vs 21% difference, i.e. an OR of 0.76), then this treatment group will be discontinued as it is futile.
- 2) IF a HBOT treatment group proves to decrease amputation rate significantly by >15% (26% vs 11%; OR: 0.352) as compared to controls, then superiority of a treatment arm is proven and the trial will be discontinued as it has reached its aim. If more than one HBOT-treatment arm shows this superiority, the group with the lowest number of HBOT treatments is deemed superior.
- 3) If the HBOT group(s) show(s) minor improvements in amputation rate (between 5% and 15%) over control, then these groups will continue in the second stage of the trial.

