#### 7.1.1 Main study parameter/endpoint

- Major amputation rate (above ankle) and (major) amputation-free survival after 12 months of follow-up

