#### 7.1.2 Secondary study parameters/endpoints (if applicable)

- Complete wound healing
- Time to reach complete wound healing
- Freedom from minor amputation (below ankle)
- Pain score (VAS)
- Health-related quality of life scores
  - EQ-5D-5L
  - SF-12
  - Vascuqol-6
- Costs related to HBOT and conventional therapy during follow-up period
- Patients' out of pocket expenses related to disease or treatment (travel expenses etc.)
- Mortality
- Patients' perception of improvement (through one anchor question)
- Forefoot TcpO2 before, during and after (HBOT) treatment (if equipment is available)

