## 9. STATISTICAL ANALYSIS

All analyses will be conducted according to the intention-to-treat principle. Baseline characteristics are summarized with descriptive statistics. Differences between dichotomous variables (like the amputation rate) will be expressed as a risk differences and Numbers Needed to Treat or Harm. Statistical precision will be expressed as 95% confidence intervals. Differences between continuous variable will be expressed as difference in means. If outcome parameters are unevenly distributed, they will be expressed as medians and inter-quartile ranges.

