### **9.3 Interim analysis**

After inclusion of 68 patients in each group and three months of follow-up, an interim analysis will be conducted (see figures 1 and 2). From our previous trial (Santema 2018) we know that the vast majority of amputations occurs within three months of follow-up. Whether and how the trial will continue will depend on the outcome of the interim analysis, which is the main feature of the MAMS study design. This is described in chapter 4.4.

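### Time to complete wound healing is fixed as Kaplan-Meier and log-rank without treating major amputation and death as competing events, which can hide an HBOT gain in healed feet

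*Protocol*

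**What the plan says.** Section 7.1.2 lists "Time to reach complete wound healing" as a secondary endpoint, separately from complete wound healing as such. For the time endpoint, section 9.2 fixes the method: "Time to complete wound healing will be estimated using Kaplan-Meier survival analysis and differences between the groups will be analysed using the log-rank test". The Cox regression mentioned there is for confounders, not for competing events.

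The event that rules out healing of the target ulcer is the trial's own primary endpoint, given in section 7.1.1 as "Major amputation rate (above ankle) and (major) amputation-free survival after 12 months of follow-up". Section 4.4 plans for 26% amputations in control and 11% with HBOT, and section 9.3 states that "the vast majority of amputations occurs within three months of follow-up". Section 1 cites a meta-analysis that found fewer major amputations with HBOT but "shows no effect on minor amputation, CUH, or mortality" (CUH is complete ulcer healing).

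Section 9 adds: "All analyses will be conducted according to the intention-to-treat principle". It reports dichotomous outcomes as risk differences with 95% confidence intervals. Death and amputation are combined in amputation-free survival, but only for the primary endpoint.

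**The concern.** Kaplan-Meier and log-rank deal with patients who leave the risk set by censoring. A censored patient is taken to have the same future chance of healing as those still at risk. For an ordinary loss to follow-up that may be reasonable. For a patient whose leg has been amputated, or who has died, that future chance is zero.

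Two things follow. First, 1-KM estimates healing in a hypothetical setting where nobody is amputated or dies, so it exceeds the share of patients who actually heal. Second, the excess grows with the number of amputations and is therefore larger in control. If HBOT saves feet and some of them then heal, the curve can miss that gain.

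At stake is the reading of the healing result. The competing event here is frequent, early and expected to differ by 15 points between arms. With the evidence cited in section 1 (fewer amputations, no effect on healing), a reader will want to know whether saved feet heal, and the planned curve does not answer that.

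**Working it through.** The protocol gives no figure for time to healing, so there is none to reproduce. The design numbers do reproduce: 68 per group per stage × 4 groups × 2 stages = 544, and 2 × 68 = 136 per group for an arm that runs through both stages.

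**Inputs from the protocol.** Major amputation by 12 months 26% (control) and 11% (HBOT); most amputations within three months.

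**Assumptions.** Net 12-month healing p of 30%, 50% or 70% (healing if nobody were amputated or died); the same healing hazard in both arms; deaths 0% or 10% in each arm; where early timing is modelled, 80% of amputations in months 0 to 3.

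**Step 1: constant hazards, no deaths.** The healing hazard is h = −ln(1 − p)/12. The amputation hazard a is solved so that 26% or 11% are amputated by month 12. Then

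- 1-KM with amputees censored = 1 − exp(−12h) = p in both arms;
- actual healing (cumulative incidence) = h/(h + a) × [1 − exp(−12(h + a))].

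For p = 50%, h = 0.05776.

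- Control, a = 0.03612: 0.05776/0.09388 × [1 − exp(−1.1266)] = 0.6153 × 0.6759 = 41.6%.
- HBOT, a = 0.01365: 0.05776/0.07141 × [1 − exp(−0.8569)] = 0.8089 × 0.5755 = 46.6%.

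| Net healing p | 1-KM, both arms | Actual, control | Actual, HBOT | Hidden gain |
|---|---|---|---|---|
| 30% | 30% | 25.4% | 28.1% | 2.7 points |
| 50% | 50% | 41.6% | 46.6% | 5.0 points |
| 70% | 70% | 56.7% | 64.6% | 7.8 points |

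(Differences are taken before rounding.)

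**Step 2: early amputations and 10% deaths.** The same formula is applied to months 0 to 3 and 3 to 12 in turn, the second interval weighted by the share still at risk at month 3. For p = 50% this gives 13.7 + 22.2 = 35.9% in control and 14.9 + 27.4 = 42.3% with HBOT, a gain of 6.3 points before rounding. For p = 30% it is 21.9% against 25.6% (3.7 points), and for p = 70% it is 49.1% against 58.4% (9.2 points). 1-KM again shows no difference. Over both steps the hidden gain is about 3 to 9 points.

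**Step 3: size of the overstatement when actual healing is equal.** With the step 2 assumptions and 40% actually healed in each arm, 1-KM gives 56% in control and 47% with HBOT. It is too high by 16 and 7 points. To reach equal healing with fewer amputations, the HBOT healing hazard has to be 0.78 of control.

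**Step 4: amputations concentrated in slow healers.** Simulation of 2,000 trials, 136 per arm. HBOT has no effect on any ulcer's healing hazard; 40% of patients are slow healers; the others heal with net probability 60%. Differences are HBOT minus control.

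| Share of amputations in slow healers | Their net healing | 1-KM difference | Actual difference | Censored log-rank significant against HBOT |
|---|---|---|---|---|
| 40% (no concentration) | 5% | 0.0 | +4.2 | 2.4% |
| 70% | 20% | −2.3 | +3.3 | 5.1% |
| 100% | 5% | −5.5 | +0.8 | 10.5% |

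The nominal rate in the last column is 2.5%. With 70% to 100% concentration and slow-healer healing of 5% to 20%, the censored log-rank has mean Z of −0.3 to −0.8. Keeping amputees at risk as unhealed to month 12, as Gray's test does, gives mean Z of +0.1 to +0.5.

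**The case against.** Four points can be made for the plan.

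1. *The protocol nowhere says that amputees and deaths are censored.* Keeping them as unhealed to month 12 would also fit the text and remove the bias, and a statistical analysis plan may settle it. This stands in part. The point therefore rests on the method that section 9.2 names, whose usual use is with censoring, and not on the absence of a detailed rule.

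2. *Log-rank with censoring is a valid test.* This stands. It tests the cause-specific healing hazard: how fast ulcers heal among patients alive with the leg. It should be kept, but labelled as that and not as a comparison of the chance of healing.

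3. *An all-randomised measure is already planned.* This largely stands. Complete wound healing is a separate endpoint, under intention to treat and with risk differences, and can show a gain that the curve misses. It does so only if amputees and deaths count as not healed.

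4. *The endpoint is secondary.* This stands. The primary endpoint, interim rules and sample size do not depend on it.

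A reader might infer something stronger: that a limb benefit of HBOT automatically turns into apparent harm on healing, with the log-rank often wrongly favouring control. The documents do not support that. With equal healing hazards and amputation unrelated to healing potential, the 1-KM difference is zero: a benefit is masked, and no harm appears. In the equal-healing case of step 3, the HBOT healing hazard is truly 0.78 of control, so a log-rank result in favour of control is a correct finding about that hazard, not a false positive. Reversal without any slowing of healing needs the saved limbs to be mainly slow healers. That is plausible, but the protocol neither states nor quantifies it, and at 136 per arm it would seldom reach significance (5% to 11% of trials).

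**Conclusion.** The concern holds in a limited form. Section 9.2 names an estimator that, as normally used, does not give the probability of healing in a trial where the primary endpoint itself prevents healing. The bias is largest in the arm with more amputations. Under the planned 26% against 11%, it can hide a gain of about 3 to 9 points in healed feet. If the limbs saved are mainly slow healers, it can show HBOT as 2 to 5.5 points worse when it is 1 to 3 points better.

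The amputation rates come from the protocol. Net healing rates, deaths, the 80% share of early amputations and the slow-healer split are assumptions, so the sizes are ranges and not forecasts. This is a worthwhile low-cost improvement to a secondary analysis, not a condition for the trial to be sound.

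**What to change.** In section 9.2:

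- Estimate time to complete healing by cumulative incidence (Aalen-Johansen) among all randomised patients, with major amputation of the target limb and death as competing events. Ordinary loss to follow-up stays censored.
- Compare arms with Gray's test, and report the cause-specific healing hazard (log-rank or Cox) alongside, labelled as such.
- In the 12-month complete-healing proportion already planned, count amputees and deaths as not healed.

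The cost is wording: healing, amputation and mortality are already collected. Healing percentages will be lower than Kaplan-Meier figures from earlier trials, and the report should say why. The change should be made before results by arm are seen, since the choice of method can affect which way the healing result points.
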